7.2 Endpoints

7.2.1 Primary endpoints

Safety and tolerability:

Clinically significant changes in: vital signs (heart rate, blood pressure, respiratory rate, pulse oximetry and temperature), 12-lead ECG, FEV₁, FVC, physical examination, nasal examination, laboratory safety tests (haematology, biochemistry and urinalysis), tolerability questionnaire, AEs and serious AEs (SAEs). Safety endpoints will be assessed up to 7 days after dosing in Part A or up to 14 days after the last dose in Part B.

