Laboratory assessments (haematology, biochemistry and urinalysis), physical examinations, 12-lead ECGs, vital signs (heart rate, blood pressure, respiratory rate, pulse oximetry and temperature), nasal examinations and spirometry will be done before and during dosing and frequently until the subject's last visit in each study part. Subjects will complete a tolerability questionnaire post-dose after each dose of Neumifil. AEs will be recorded from screening until the subject's last visit in each study part.

The schedules of procedures are in sections 12.1.1 (Part A) and 12.1.2 (Part B).

Laboratory safety variables to be assessed during the study are in Table 7.

Throughout the study, AEs and concomitant medication will be documented as they are reported by the subjects. Subjects will be questioned about AEs when procedures are done, and when they return to the ward for outpatient visits (Part B only), and at follow-up.

Plasma concentration of Neumifil

Blood samples for assay of Neumifil will be taken before and up to 3 h after dosing on Day 1 (Part A) and Days 1 and 7 (Part B).

[figure not shown]
Immunogenicity

Blood samples for assay of Neumifil ADAs will be taken before dosing on Day 1 and on Day 22 (Part B only).

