12.1 Schedule of procedures

12.1.1 Part A

Period:	Screening 1	Study session											Follow-up			
		Day:	-35 to -2	-1	Pre	0	0.25	0.5	1	2	2.5	3	4	8	12	24
Time (h)																
Informed consent	X															
Inclusion/exclusion criteria	X	X	X													
Medical history	X															
Admission		X														
Inpatient stay			◀											▶		
Discharge																X
Safety assessments																
Physical examination ²	X	X							X							X
Height & weight ³	X	X														X
Vital signs ⁴	X	X	X						X			X	X	X	X	X
12-lead ECG ⁵	X		X							X						X
Serology	X															
Laboratory safety tests ⁶	X	X	X										X		X	X
Pregnancy ⁷	X	X														X
FSH ⁸	X															
Urine drug, alcohol and cotinine tests	X	X														
Spirometry ⁹	X											X	X	X	X	X
Nasal examination	X	X														X
SARS-CoV-2 infection test ¹⁰	X	X														X
Self-assessment nasal tolerability rating scale								X								X
Dosing																
Intranasal Neumifil					X											
Neumifil PK																
PK sampling ¹¹				X					X	X		X				

Abbreviations: ECG: electrocardiogram; FSH: follicle-stimulating hormone; PK: pharmacokinetics; AEs: adverse events.

Notes:

1. Screening will be within 35 days before dosing
2. Full physical examinations will be done at screening and on Day -1. Brief (symptom-directed) physical examinations will be done at all other timepoints.
3. Height measured at screening only.
4. Vital signs consist of: systolic and diastolic blood pressure, heart rate, pulse oximetry, temperature and respiratory rate. They will be assessed at screening; on Day -1, and before and at 2, 4, 8, 12 and 24 h after dosing on Day 1; and at follow-up. Triplicate measurements (at least 2 min apart) will be made at screening and before dosing. Single measurements will be made at all other time points. Measurements should be made with subjects in a supine position, after resting for 5 min.
5. ECGs will be recorded at screening; before and at 2.5 h after dosing on Day 1; and at follow-up. Triplicate recordings (at least 2 min apart) will be made at screening and before dosing; single recordings will be done at all other time points. Recordings should be made with subjects in a supine position, after resting for 5 min.

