6. ECGs will be recorded at screening; before and at 2.5 h after dosing on Days 1 and 7; and at follow-up. Triplicate recordings (to at least 2 min apart) will be made at screening; single recordings will be done at all other time points. Recordings should be made with subjects in a supine position, after resting for 5 min.
7. Laboratory safety tests consist of biochemistry, haematology and urinalysis in serum. They will be done at screening; on Day –1; at 24 h after dosing on Day 1; on Day 8; at the outpatient visit; and at follow-up. Subjects should fast for \geq 8 h before laboratory safety tests at screening, admission (Day –1), and follow-up.
8. Pregnancy tests in women of child-bearing potential only.
9. FSH tests in post-menopausal women at screening only.
10. FEV₁ and FVC will be measured at screening; at 4, 8, 12 and 24 after dosing on Days 1 and 7; at the outpatient visit; and at follow-up.
11. If a subject develops symptoms of COVID-19, ad hoc SARS-CoV-2 infection tests will be done.
12. Self-assessment nasal tolerability questionnaires will be completed at 1 and 12 h post dose after each dose of Neumifil.
13. Once-daily intranasal doses of Neumifil.
14. Blood samples for assay of Neumifil will be taken:
 - before and at 1, 2, and 3 h after dosing on Days 1 and 7
15. Blood samples for assay of Neumifil ADAs will be taken before dosing on Day 1, and at follow-up.
16. Nasal wick samples will be taken before the evening meal on Day –1, or not less than 2 h after food at all timepoints.

When more than one procedure is scheduled at a specific time point, procedures should be done in the following order: ECG, vital signs, blood samples (at the scheduled time), then spirometry. Blood sampling should be done on time. Other procedures should be done as close as possible to the scheduled time point.

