16.1.4 General considerations for data analyses

The minimum set of summary statistics for numeric variables will be: n, mean, standard deviation (or standard error), median, minimum, and maximum. 95% confidence intervals will be presented where appropriate for data interpretation.

Categorical data will be summarised in frequency tables with n and percentage. Summaries of a categorical variable will include all recorded values.

The minimum and maximum values will be presented to the same number of decimal places as the raw data collected in the CRF (or to 3 significant figures for derived parameters). The mean, median and percentiles (eg Q1, and Q3) will be presented to one additional decimal place. The standard deviation and standard error will be presented to 2 additional decimal places.

'Baseline' will be the latest value obtained before IMP administration (predose on Day 1, or Day -1 if not recorded at predose, or screening if not recorded at predose or on Day -1 [eg weight]). Out-of-range laboratory tests may be repeated. If a test is out of-range at baseline and repeated before dosing, the latest repeat value before dosing will be used as baseline. However, if a test is out-of-range and repeated at any other time during the study, the out-of-range value (not the repeat value) will be included in statistical summaries.

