17. The Human Medicines (Amendment etc) (EU Exit) Regulations 2019: Statutory instrument 2019 No 775.
18. The Human Medicines (Amendment etc) (EU Exit) Regulations 2020: Statutory instrument 2019 No 1488.
19. Standard operating procedures for Research Ethics Committees in the UK, Research Ethics Service.
20. Structure and content of clinical study reports. ICH harmonised tripartite guideline E3, 1995.
21. Guidelines for Phase 1 Clinical Trials, 2018 Edition. Association of the British Pharmaceutical Industry.

22 Appendix 1: Subject self-reported dosing and post-dosing experience

Study PNG-NMF-101

Subject Number:

Please assess the following aspects of your dosing and post dosing experience, following administration of Neumifil or placebo. A numerical score of 0 to 10 is used for each parameter, as described below

The statements are as follows.

Since your last dose have you experienced any of the following? –

1. Pain or stinging in the nose?

Score

0 No Pain or stinging in the nose has been experienced

10 Pain or stinging most extreme imaginable and you would not want to experience it again

2. Burning sensation or sensation of heat/hotness in the nose?

Score

0 No Burning sensation or sensation of heat/hotness in the nose has been experienced

10 Burning sensation or sensation of heat/hotness in the nose most extreme imaginable and you would not want to experience it again

3. Bleeding from the nose.

Score

0 Bleeding has not experienced

10 Bleeding that requires medical intervention and packing of the nose.

4. Sensation of needing to blow your nose?

Score

0 The sensation of needing to blow your nose has not been experienced

10 The sensation to blow your nose is persistent and affects your normal life to the extent you would not want to experience it again

5. General irritation in nose.

Score

0 No irritation has been experienced

10 Irritation of the nose is the most extreme imaginable and you would not want to experience it again

6. Sneezing**Score**

0 Sneezing is not experienced

10 Sneezing most extreme imaginable and you would not want to experience it again

7. Marked change in your sense of smell or taste**Score**

0 No change in your sense of smell or taste

10 Complete loss of smell or taste

8. Unpleasant taste.**Score**

0 No unpleasant taste

10 Unpleasant taste is so bad you would not want to experience it again

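### The nasal tolerability questionnaire has no pre-dose score, so symptoms already present at dosing can be counted as treatment-emergent

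*Combined protocol and SAP*

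**What the plan says.** Section 7.2.1 (and the matching summary, 2.3.1) opens the primary endpoint with "Clinically significant changes in: vital signs (heart rate, blood pressure, respiratory rate, pulse oximetry and temperature" and carries the list on to "laboratory safety tests (haematology, biochemistry and urinalysis), tolerability questionnaire, AEs and serious AEs (SAEs".

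On timing, the safety and tolerability text of section 12 says: "Subjects will complete a tolerability questionnaire post-dose after each dose of Neumifil". For Part B, note 12 to the schedule in 12.1.2 says: "Self-assessment nasal tolerability questionnaires will be completed at 1 and 12 h post dose after each dose of Neumifil". In the Part A schedule (12.1.1) the row "Self-assessment nasal tolerability rating scale" shows marks only after the dosing mark. The form itself, in Appendix 1 (section 22), asks: "Since your last dose have you experienced any of the following".

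Baseline is defined in 16.1.4: it "will be the latest value obtained before IMP administration", taken from predose on Day 1, otherwise Day -1, otherwise screening.

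Three other places decide how the scores are used:
- Section 14.2 turns any questionnaire score above 0 into an AE.
- Section 16.1.6.1 defines a treatment-emergent AE as one that was not there before treatment or that became worse after it.
- Section 8.5.1 puts the questionnaire among the data that the Safety Review Group must see before each dose decision.

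Section 16 names no summary, listing or change-from-baseline analysis for the questionnaire.

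**The concern.** The product is intranasal and first-in-human, and this form is the subjects' own graded report of local tolerability. It is the only measured assessment under the section 7.2.1 heading with no value before dosing. Vital signs, ECG, spirometry, laboratory tests, and physical and nasal examinations all have one.

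The consequence goes beyond the endpoint wording. After dosing, subjects are prompted on eight named symptoms, and any non-zero answer becomes an AE. Before dosing, they get only a general, non-leading AE enquiry and a few nasal questions. A minor symptom that was there all along, such as an urge to blow the nose, is more likely to be recorded after the dose than before it. It would then look new. Whether a symptom became worse cannot be judged on the 0 to 10 scale that generated the AE.

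At stake are the content of the treatment-emergent AE tables and the blinded Safety Review Group's ability to tell pre-existing symptoms from new ones.

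**Working it through.** The plan gives no power, alpha or expected rate for this measure (16.1.2 and 16.2 state no hypotheses and no formal sample size), so there is no planned figure to reproduce. The check is a count and a comparison of sections.

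**1. Completions before the first dose.** Part A: 0. Part B: 0. On the planned once-daily schedule, Part B has 2 × 7 = 14 post-dose forms per subject. The Part A columns are displaced in the extracted table, so I do not rely on the exact hours; the section 12 text settles that completion is post-dose.

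**2. Scores that meet the 16.1.4 baseline.** None at predose, Day -1 or screening. A change from a pre-dose score is available for 0 of 36 + 24 = 60 planned subjects.

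**3. What each score measures.** Seven of the eight items ask whether a symptom was experienced since the dose, not whether it began then. A subject with the symptom beforehand would truthfully score above 0. Only item 7 (smell or taste) rates a change directly.

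**4. From score to treatment-emergent AE.** 14.2: score above 0 → AE. 16.1.6.1: AE → treatment-emergent if absent before or worse after. The second step needs the pre-dose state, and no form records it on this scale.

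**5. What partly stands in for a baseline.**

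| Source | Helps with | Does not give |
|---|---|---|
| AE recording from screening (12, 14.2) | Symptoms the subject volunteers | Prompted items; a 0 to 10 grade |
| Exclusion criterion 6 (9.3) | Respiratory-illness symptoms, including runny nose and sneezing, at screening or before dosing on Day 1 | A score; every questionnaire item |
| Nasal examination at screening and Day -1 (12.4, schedules) | Tenderness, soreness, irritation, smell | A score; specific questions on burning, urge to blow the nose or unpleasant taste |
| Placebo subjects | Background rate by arm, once unblinded | A within-subject reference; any reference during blinded review |

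**6. Placebo numbers.** Part A, groups A1–A5: 2 + 2 + 2 + 3 + 3 = 12. Part B, groups B1–B3: 2 × 3 = 6. Suppose none of them scored above 0. The exact upper 95% limit for the background proportion is 1 − 0.025^(1/n):
- n = 12: 1 − 0.025^(1/12) = 26.5%
- n = 6: 1 − 0.025^(1/6) = 45.9%

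This pools placebo across groups within a part, which is an assumption. It shows only how loosely the placebo arm can pin down the background.

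**The case against.** The strongest case against has four parts.

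- **No planned analysis fails.** The change heading in 7.2.1 also covers AEs and SAEs, which have no baseline score, and section 16 plans change from baseline for vital signs, ECG and pharmacodynamics but not for the questionnaire. This stands. A reader might infer that no change of any kind can be derived or that a primary analysis is impossible. The documents do not support that: item 7 is itself a change item, later Part B scores can be compared with earlier ones, and the above-zero rule needs no baseline. What is missing is a change from a pre-dose score.
- **The form is post-dose by design.** True, and its stem cannot be answered before a first dose. That explains the gap but does not supply the pre-dose state that 16.1.6.1 needs.
- **Randomised placebo is the proper control for background, spray and vehicle.** It is, for the final comparison. It does not help the Safety Review Group while blinded, or the classification of one subject's event.
- **The cause and size are not documented.** This stands. A reader might infer that Day -1 nasal procedures leave symptoms at dosing. No section says so, and the sampling site of the SARS-CoV-2 test is not given. A reader might also assume a background rate per item: with eight independent items at 2%, 5% or 10%, 1 − (1 − p)^8 gives 15%, 34% or 57% of subjects with a non-zero score. Those rates have no source here, and positive correlation between nasal items would lower the results.

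A further fair warning is that a baseline with a 24-hour recall could capture symptoms already gone by dosing, and subtracting it could hide a real local effect. The fix below allows for this.

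**Conclusion.** The point holds in limited form. The questionnaire sits under a change endpoint but has no pre-dose score. Because every non-zero score becomes an AE, symptoms present at dosing can be classed as treatment-emergent, and the blinded dose reviews have no within-subject reference on the same scale. The existing safeguards reduce this without removing it.

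The count (0 of 60 planned subjects with a pre-dose score) rests on the section 12 text and note 12 and needs no assumption. How many AEs would be misclassified cannot be estimated from the documents. This is a worthwhile, inexpensive improvement; it does not invalidate the safety assessment.

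**What to change.** - **Schedule (12.1.1; 12.1.2 with note 12; section 12 text):** add one completion of the same eight items just before the first dose on Day 1 in both parts.
- **Appendix 1:** give that form its own stem about current symptoms, for example *At this moment, do you have…*, with the anchors in the same tense. Adapt item 7, for example to ask whether smell and taste are normal for the subject now.
- **16.1.4:** define this completion as the questionnaire baseline.
- **16.1.6:** add the questionnaire. Make raw post-dose scores by item, time point and treatment the main display, with change from baseline alongside. Give the Safety Review Group both, blinded.
- **14.2 and 16.1.6.1:** state that the item's pre-dose score is used to decide whether a score-based AE is treatment-emergent, that is, absent before dosing or worse after it. All scores above 0 would still be recorded as AEs.

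The cost is one short form per subject (60 if all planned groups enrol, excluding replacements and optional groups), a schedule mark and an appendix edit, with no new visit or procedure. The recall windows before and after dosing will differ slightly, which is why the raw scores should lead. The change has to be in place before dosing, because the missing score cannot be recovered later.

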7.2.2 Exploratory endpoint

Safety: SARS-CoV-2 infection test, done at screening, before the first dose, on Day 8 (Part B only), and at follow-up.

Immunogenicity: ADAs of Neumifil, as assessed by IgA and IgG concentration, derived from blood samples taken before the first dose and at Follow-up (Part B only).

Plasma concentration of Neumifil: Plasma concentrations of Neumifil after single doses on Day 1 in Part A, and after dosing on Days 1 and 7 in Part B.

Cytokine and chemokine concentrations in nasal secretions: Presence and concentration of cytokines and chemokines, measured by multiplex assay, in nasal wick samples collected on Day -1, Day 8, and at follow up (Part B only).

8 Overall trial design

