2.3 Endpoints

2.3.1 Primary endpoints

Safety and tolerability:

Clinically significant changes in: vital signs (heart rate, blood pressure, respiratory rate, pulse oximetry, and temperature), 12-lead electrocardiogram (ECG), forced expiratory volume (FEV₁), forced vital capacity (FVC), physical examination, nasal examination, laboratory safety tests (haematology, biochemistry and urinalysis), tolerability questionnaire, number and severity of adverse events (AEs) and serious AEs. Safety endpoints will be assessed up to 7 days after dosing in Part A or up to 14 days after the last dose in Part B.

2.3.2 *Exploratory endpoint*

PD: SARS-CoV-2 infection test, done at screening, before the first dose, on Day 8 (Part B only), and at follow-up.

Immunogenicity: ADAs of Neumifil, as assessed by immunoglobulin A and G (IgA and IgG) concentration, derived from blood samples taken before the first dose and at follow-up (Part B only).

Plasma concentrations of Neumifil: Plasma concentrations of Neumifil after single doses on Day 1 in Part A, and after dosing on Days 1 and 7 in Part B.

Cytokine and chemokine concentrations in nasal secretions: Presence and concentration of cytokines and chemokines, measured by multiplex assay, in nasal wick samples collected on Day –1, Day 8, and at follow up (Part B only).

2.4 *Type of trial*

This is a Phase 1, single-centre, randomised, placebo-controlled first-time-in-human (FTIH) study in healthy subjects. The study is in 2 parts and will investigate single-ascending (Part A) and multiple-ascending (Part B) doses of Neumifil, administered intranasally.

2.5 *Trial design and methods*

2.5.1 *Part A*

Part A is a randomised, double-blind, placebo-controlled, single ascending dose study. Enrolment of up to 36 healthy subjects is planned, in up to 5 groups (Groups A1–A5). Groups A1–A3 will consist of 6 subjects each and Groups A4 and A5 will consist of 9 subjects each.

Subjects will receive a single intranasal dose of Neumifil or placebo. In Groups A1–A3, 4 subjects will receive Neumifil and 2 will receive matching placebo. In Groups A4 and A5, 6 subjects will receive Neumifil and 3 will receive matching placebo.

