Neumifil is a potential medication against SARS-CoV-2 infection, although this study is in healthy volunteers and no benefit is expected. Preliminary non-clinical data indicate that Neumifil can protect recipient animals (Syrian hamster) against infection by SARS-CoV-2 and therefore no specific risks to participants due to conducting the study during the COVID-19 pandemic are anticipated. Non-clinical work in mice, has shown that pre-treatment of mice with Neumifil, before a lethal influenza challenge, protects mice from the viral challenge and does not reduce the development of protective immune responses against the influenza strain. Therefore, it is not anticipated that Neumifil will attenuate the immune response to a vaccine. No interaction between Neumifil and vaccinations against COVID-19 are anticipated.

The purpose of this study is to assess safety and tolerability of Neumifil; to avoid an overlap of adverse events, the administration of Neumifil will not be within 7 days of

a vaccination against COVID-19. Subjects will be resident in the HMR Phase 1 unit for the dosing period. Avoiding administering Neumifil within 7 days of a COVID-19 vaccination will mean subjects in Part A will have a 14-day window (Day -7 to Day 8 with dosing on Day 1) when they will not be eligible for the study if they have a COVID-19 vaccination booked. In Part B there will be a 21-day window (Day -7 to Day 15 with dosing on Day 1) when they will not be eligible for the study if they have a COVID-19 vaccination booked.

This clinical trial will be done in accordance with HMR's COVID-19 risk mitigation policy (RMP), which documents HMR's COVID-19 virus testing strategy for volunteers and staff, social distancing measures, and management of COVID-19-like symptoms. HMR's RMP was first notified to the MHRA and Health Research Authority (HRA) on 22 May 2020, and applies across all HMR's trials. The mitigation measures specified in the HMR COVID-19 RMP are deemed adequate for this trial. Any deviations from the RMP will be documented in a separate COVID-19 trial-specific risk assessment, prepared by the investigator. Any deviations from the protocol that result from the COVID-19 pandemic, and COVID-19 related AEs or SAEs, will be documented.

Taking the above factors into account, and the proposed mitigation, we believe that it is medically and ethically acceptable to proceed with the trial during the current COVID-19 pandemic.

7 Objectives and endpoints

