7.1.2 Exploratory objective

- To determine the number of subjects contracting SARS-CoV-2 during the 7 days after receiving their (last) dose.
- To assess the formation of Neumifil ADAs after multiple-ascending intranasal doses in healthy subjects (Part B only).

- To assess the plasma concentration of single- or multiple-ascending intranasal doses of Neumifil in healthy subjects to determine if intranasal administration results in systemic exposure.
- To assess the concentrations of cytokines and chemokines in nasal secretions before dosing and after multiple intranasal doses of Neumifil (Part B only).

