9.3 Exclusion criteria

1. Woman who is pregnant or lactating, or pre-menopausal woman who is sexually active and not using a reliable method of contraception (see section 11).
2. Clinically relevant abnormal medical history, physical findings, ECG, or laboratory values at the pre-trial screening assessment that in the opinion of the

investigator could interfere with the objectives of the trial or the safety of the volunteer.

3. Presence or history of acute or chronic illness sufficient to invalidate the volunteer's participation in the trial or make it unnecessarily hazardous.
4. Presence or history of respiratory disease, including (but not limited to) asthma, chronic obstructive pulmonary disease (COPD), cystic fibrosis, emphysema, requiring acute or chronic medication.
5. Presence of nasal polyps or significant nasal abnormalities.
6. Symptoms of respiratory illness (including, but not limited to, runny nose, sore throat, sneezing, coughing or wheezing) at the screening visit or before dosing on Day 1.
7. Tympanic temperature $> 37.5^{\circ}\text{C}$ at the screening visit or before dosing on Day 1.
8. Impaired endocrine, thyroid, hepatic, respiratory or renal function, diabetes mellitus, coronary heart disease, or history of any psychotic mental illness.
9. History of psychiatric disease, as determine by the investigator.
10. History or presence of malignant disease.
11. Immune-suppressed status, resulting from either disease or medication, as determined by the investigator.
12. Presence or history of severe adverse reaction to any drug or the excipients of Neumifil.
13. Known allergy to tetracycline antibiotics.
14. Use of a prescription medicine (except HRT in female subjects), including oral contraceptives, during the 28 days before the first dose of trial medication, or use of an over-the-counter medicine, with the exception of acetaminophen (paracetamol) and vitamin or nutritional supplements, during the 7 days before the first dose of trial medication.
15. Receipt of an investigational product (including prescription medicines) as part of another clinical trial within the 3 months before admission to this study; in the follow-up period of another clinical trial at the time of screening for this study.
16. Receipt of a COVID-19 vaccine within 7 days before the first dose of trial medication, or anticipate receiving a COVID-19 vaccine within the 7 days after a (final) dose of trial medication.

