Women of childbearing potential must use a highly effective method of contraception with low-user dependency during the trial, and for up to one month after the final follow up visit. They must have been using that method for at least 28 days before the start of the trial. Highly effective methods of contraception include:

- Progestogen-only hormonal contraception implants associated with inhibition of ovulation
- Intrauterine device (IUD)

- Intrauterine hormone-releasing system (IUS)
- Bilateral tubal occlusion or ligation
- Vasectomised partner (with surgical success confirmed by medical assessment)

A woman is considered to be of non-childbearing potential if she meets one of the following criteria:

- is post-menopausal (the last menstrual period was at least 12 months ago, and Follicle Stimulating Hormone (FSH) test at screening confirms post-menopausal status)
- has no uterus, ovaries or fallopian tubes

Women who are taking HRT must use contraception (as described above) during the trial unless prescribed following bilateral oophorectomy, hysterectomy or salpingectomy.

Combined or progesterone-only hormonal contraception associated with inhibition of ovulation (oral, intravaginal, transdermal or injections) are not allowed.

Subjects who practise true abstinence or who only have same-sex relationships need not use contraception, provided it is in line with their preferred and usual lifestyle (note: periodic abstinence [eg calendar, ovulation, symptothermal, and post-ovulation methods] and withdrawal are not acceptable methods of contraception). Should any such subject stop practising true abstinence, they must use contraception as described above.

12 Procedures and observations

Only subjects who meet all the inclusion and no exclusion criteria will be eligible for enrolment into the trial (see section 9). Each subject will be allocated a unique trial number (see section 10.5).

Additional time points may be introduced, and changes to time points may be made, in accordance with section 12.2.

The following assessments will be made at the timepoints given in sections 12.1.1 (Part A) and 12.1.2 (Part B).

Safety and tolerability

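### Does the Part B SARS-CoV-2 endpoint lose its outpatient test, and do visit labels that run one day late matter?

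*Combined protocol and SAP*

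**What the plan says.** The objective in section 7.1.2 is "To determine the number of subjects contracting SARS-CoV-2 during the 7 days after receiving their (last) dose". Section 7.2.2, under the label Safety, gives the test times as "SARS-CoV-2 infection test, done at screening, before the first dose, on Day 8 (Part B only), and at follow-up". The summary in section 2.3.2 gives the same times under a different label: "PD: SARS-CoV-2 infection test, done at screening, before the first dose, on Day 8 (Part B only), and at follow-up".

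The Part B schedule (section 12.1.2) has five marks in the SARS-CoV-2 row, and its note 11 adds unscheduled tests for anyone with COVID-19 symptoms. Section 12 states which text directs the work: "The following assessments will be made at the timepoints given in sections 12.1.1 (Part A) and 12.1.2 (Part B").

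Sections 2.5.2 and 8.1.2 place the Part B outpatient visit 7–8 days after the last dose and label it Days 15–16. They place follow-up at 13–15 days and label it Days 21–23. The schedule heads these columns 14 to 16 and 21 to 23, and its note 2 sets follow-up at 14 ± 1 days. Table 6 allows ± 1 day for outpatient visits without a protocol deviation.

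On vaccination, section 6.5.1 says "In Part B there will be a 21-day window (Day -7 to Day 15 with dosing on Day 1"). Exclusion criterion 16 bars subjects who "anticipate receiving a COVID-19 vaccine within the 7 days after a (final) dose of trial medication", and section 10.7 repeats the 7-day rule without day numbers.

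**The concern.** Read alone, the endpoint text leaves Part B with post-dose tests about 1 day and about two weeks after the last dose, and none near day 7, where the objective's window closes. An asymptomatic infection first found at follow-up could then not be placed inside or outside the window, so the count in the objective would be undefined for that subject. The two labels add doubt about which analysis population applies, and section 16 names no analysis of this test.

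The day labels raise a related doubt. If 7 days after the last dose is Day 14 in one section and Day 15 in another, an infection or a vaccination on Day 15 could be classified either way.

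**Working it through.** **Is the outpatient test scheduled?** The table was extracted from PDF, so the column has to be inferred. Each row has 12 cells. The notes show what cell 11 stands for.

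| Row | Marked cells | Post-discharge visits named in the text |
|---|---|---|
| Laboratory tests | 1, 2, 4, 9, 11, 12 | note 7: outpatient and follow-up |
| Vital signs | 1, 2, 3, 4, 9, 10, 11, 12 | note 5: outpatient and follow-up |
| Spirometry | 1, 3, 4, 9, 10, 11, 12 | note 10: outpatient and follow-up |
| ECG | 1, 3, 9, 12 | note 6: follow-up only |
| Nasal wick | 2, 9, 12 | section 7.2.2: follow-up only |
| SARS-CoV-2 | 1, 2, 9, 11, 12 | endpoint text: follow-up only |

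In the first five rows, cell 11 is marked exactly when the text names the outpatient visit. The SARS-CoV-2 row is marked there too, so five tests are scheduled against four in the endpoint text. Days 7 and 8 are not cleanly separated in the extracted table, but that does not affect cell 11.

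**Day labels.** The visit day is the day of the last dose plus the interval.

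- Part A check, dose on Day 1: 1 + 7 = 8 and 1 + 8 = 9. This gives Days 8–9, as stated in section 8.1.1.
- Part B, seven once-daily doses from Day 1: the last dose is on Day 7, and 7 + 1 = 8 agrees with the Day 8 label for 24 h after the last dose.
- Outpatient: 7 + 7 = 14 and 7 + 8 = 15, against a text label of 15–16. The schedule's 14–16 is 7 to 9 days after the last dose, so only its upper end is late.
- Follow-up: 7 + 13 = 20 and 7 + 15 = 22, against 21–23 in the text and the schedule header.
- Counting from Day 8 reproduces the text labels: 8 + 7 = 15, 8 + 8 = 16, 8 + 13 = 21, 8 + 15 = 23. That is a simple miscount.

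**Vaccination window** (no Day 0). Part A in elapsed days: 7 + 7 = 14, as stated. Part B in elapsed days: 7 before the first dose, 6 from first to last dose and 7 after gives 20, ending on Day 14. Section 6.5.1 says 21, ending on Day 15. Counted inclusively, Day –7 to Day 14 is 7 + 14 = 21 calendar days, although the same count gives 7 + 8 = 15 for Part A. The length therefore depends on the counting convention. The end day is the firmer discrepancy.

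**What the outpatient test does for the count.** The window closes on Day 7 + 7 = 14. For a subject negative on Day 8:

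- If only follow-up is used, a new positive spans 20 − 8 = 12 to 23 − 8 = 15 days, of which 14 − 8 = 6 lie in the window.
- With the outpatient test on Days 14–16, a new positive at that visit spans 14 − 8 = 6 to 16 − 8 = 8 days and overruns the window by at most 16 − 14 = 2 days.
- If the ± 1 day in Table 6 comes on top of those labels, the visit may fall on Day 17 and the overrun is at most 17 − 14 = 3 days.

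The 12–15 day span arises only if a test that the schedule requires is left unused.

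**The two labels.** Under section 16.1.3 the PD population is the safety population restricted to subjects with a PD measure. The schedule tests every subject before dosing. If this test counts as a PD measure, every dosed subject tested as scheduled has one, and the two populations coincide.

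**The case for a change.** The best case for a change is that the omitted test is the one the objective most needs, that section 16 is silent on the analysis so the endpoint text is the SAP author's main guide, and that the repair is a few words. Nor does the visit tolerance explain the labels: the text pairs explicit intervals with explicit days and they disagree, while Part A uses the right rule.

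All of that stands as description. It does not lead to a wrong result. A SAP author who works from the schedule will find the outpatient column, and each result can be placed by its actual days since the last dose. That also settles whether the window ends on Day 14 or Day 15, and it still works if dosing is lengthened, which section 8.5.3 allows up to 14 days and which would shift every printed day number. On vaccination, exclusion 16 and section 10.7 agree with each other. Section 6.5.1 is risk narrative and itself states the principle as 7 days, so its Day 15 is a mismatch to be reconciled with them, with no bearing on the analysis.

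**Conclusion.** The inconsistencies are genuine but clerical. One scheduled test is missing from a list, one test carries two labels, and several Part B day numbers are one day late. No scheduled data are lost, no planned analysis is wrong, and the missing counting rule is one that analysts would set sensibly in the SAP, which section 16.1.1 places before first database lock. The reach is an exploratory count, with no hypothesis attached, in up to 24 planned Part B subjects. The primary safety endpoints do not depend on it. The wording could be tidied whenever the protocol is next revised, but the conduct and analysis of the trial do not wait on that.

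This rests on two assumptions: that cell 11 of the extracted schedule is the outpatient column, as the other rows and their notes indicate, and that Part B keeps to 7 days of dosing, so that the last dose is on Day 7.
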